3.2.1.1 Primary efficacy analysis

The primary endpoint is the relative lesion count, measuring the ratio of the number of lesions detected by ⁶⁸Ga-OPS202 to the number of lesions assessed by SOT.

The SOT is the CT scan images acquired at Visit 2 and Visit 3, using number of lesions identified by the reader on both timepoints together (provided by ICL), in order to take into account potential variability within subject or partial volume effect.

For each PET/CT assessment, this ratio will be computed, as indicated below:

$$\text{Relative lesion count} = \frac{\text{Number of lesions detected by } 68\text{Ga} - \text{OPS202}}{\text{Number of lesions detected by SOT}}$$

Numerator and denominator will be available in the database provided by ICL.

Selection of the optimal dose range for peptide mass and radioactivity of ⁶⁸Ga-OPS202 will be based on the observed highest relative lesion counts, based on provided descriptive statistics: n (number of non-missing observations), number of missing values (if any), arithmetic mean, standard deviation (SD), median and the range (minimum, maximum). Those descriptive statistics will be used for analysing all continuous parameters.

Analysis over all organs

For each PET/CT and PET assessment, relative lesion count will be computed over all lesions of all organs.

The denominator, based on SOT, will be computed over all organs.

Analysis per organ

For each PET/CT and PET assessment, relative lesion count will be computed for each of the following organs:

- Primary site of GEP-NET (among all subjects with at least one lesion detected by SOT on primary site of GEP-NET).
- Lymph nodes (among all subjects with at least one lesion detected by SOT on lymph nodes).
- Liver (among all assessed subjects with at least one lesion detected by SOT on liver).

- Axial/appendicular skeleton (bones) (among all assessed subjects with at least one lesion detected by SOT in bones).
- Lungs (among all assessed subjects with at least one lesion detected by SOT in lungs).

The denominator, based on SOT, will be computed for each organ.

Relative lesion count (over all organs then per organ) will be summarised using descriptive statistics for:

- each of the six combinations of injected peptide/radioactivity dose range, presented in such a way that study arms are explicit
- each of the two peptide mass dose ranges
- each of the three radioactivity dose ranges

No statistical test will be performed (no p-value nor confidence interval).

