3.2.1.2 Secondary efficacy analysis

All secondary and exploratory analyses will be performed on PP population only.

Selection of the optimal dose range for peptide mass and radioactivity of ^{68}Ga -OPS202 will be based on the provided descriptive statistics for all secondary and exploratory efficacy endpoints, in addition to primary endpoint.

Key Secondary Endpoint:

a) Image quality

Quantitative measure:

For each PET assessment, image quality will be quantitatively measured by the tumour-to-background ratio, which will be obtained using the mean of all lesions tumour-to-backgrounds, for each of the four following organs:

- Liver
- Lymph nodes
- Bone
- Lungs

For up to five most avid lesions per organ that are confirmed by SOT, the tumour-to-background ratio will be computed as lesion SUV_{mean} divided by the SUV_{mean} of the subject's reference tissue (tumour-free liver or aortic blood).

Tumour-to-background ratio is a unit-less measure. A high tumour-to-background ratio indicates high effectiveness of ^{68}Ga -OPS202 as a diagnostic agent.

Tumour-to-background ratio will be analysed using descriptive statistics, presented for each of the four organs and for:

- each of the six combinations of injected peptide/radioactivity dose range
- each of the two peptide mass dose ranges
- each of the three radioactivity dose ranges

Individual values of tumour-to-background ratio will be listed by subject, by organ and by visit. Background location will be specified (L: Liver, B = Aortic blood).

Qualitative measure:

A qualitative analysis of the image assessed by the independent blinded readers will be performed to back up the quantitative quality measured by tumour-to-background analysis. This qualitative assessment will be performed using a quality score.

For each PET/CT and PET assessment, each independent blinded reader will perform a direct comparison of the two ^{68}Ga -OPS202 scans (Visit 2 and Visit 3, that have with different peptide and radioactivity doses). He/she will note which of the pair provides superior images based on overall image quality and lesion count, attributing a score for each assessment.

The score for the assessment having superior images will be set to “1”, and score for the assessment not selected will be set to “0”. In case of equal quality, both assessments will have a score of “1”.

Values will be available in the database provided by ICL.

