- Number of subjects having lesions detected by ^{68}Ga -OPS202 when no lesions is detected by SOT (so called “False Positive” lesions, although in this instance, without histology, this determination is equivocal), in each of five anatomic sites (Primary site of GEP-NET, Lymph nodes, Liver, Axial/appendicular skeleton (Bones), Lungs).
- Number of subjects having lesions detected by SOT when no lesions is detected by ^{68}Ga -OPS202 (so called “False negative” lesions, although in this instance, without histology, this determination is equivocal), in each of five anatomic sites (Primary site of GEP-NET, Lymph nodes, Liver, Axial/appendicular skeleton (Bones), Lungs).

Individual values of number of lesions detected by ^{68}Ga -OPS202 and difference with number of lesions detected by SOT will be listed by subject, by anatomic site and by visit for both types of assessment (PET/CT and PET),

- d) The primary and secondary endpoints will also be evaluated on a radioactivity dose/kg of body weight.

For each subject's visit, the radioactivity dose/kg (in MBq/kg) will be computed using following formula:

$$\text{Radioactivity dose/kg} = \frac{\text{Injected radioactivity dose at visit (MBq)}}{\text{Patient's weight at visit (kg)} *}$$

*In case subject's weight is not available at visit, last weight value will be used.

First, as a preliminary step, a boxplot will be drawn in order to describe subjects' weight at Visit 2, for each of 6 combinations of injected peptide/radioactivity dose range.

The following efficacy criteria will be analysed:

- Primary criterion: Relative lesion count (overall and per each of the five anatomic sites)
- Secondary criteria: Image quality (tumour-to-background ratio for each of the four organs, quality score), lesion SUV_{max} in each of the four organs, absolute number of lesions in each of the five anatomic sites, difference between number of lesions detected by ⁶⁸Ga-OPS202 and number of lesions detected by SOT.

As graphical analysis of the radioactivity dose/kg, the following plots will be performed (plot of individual values) with both peptide dose ranges shown by using two different symbols:

- Scatterplot of radioactivity dose/kg x relative lesion count, per organ and overall
- Scatterplot of radioactivity dose/kg x tumour-to-background ratio, for each of the four organs (Lymph nodes, Liver, Axial/appendicular skeleton (Bones), Lungs)
- Scatterplot of radioactivity dose/kg x quality score

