For lesion-based approach (per organ), following organs will be analysed: Primary site of GEP-NET, Lymph nodes, Liver, Axial/appendicular skeleton, Lungs. In case no lesions were detected by the SOT, sensitivity cannot be computed due to null denominator. Therefore only organs with lesions detected by SoT will be analysed for sensitivity.

To allow for computation of sensitivity, detected lesions will be counted from the “Lesion Matching Table” provided by ICL.

Additionally, an organ-based specificity analysis will be performed, based on PET/CT assessments.

For each organ:

- If there are 0 lesions detected in an organ on both ^{68}Ga -OPS202 scan and SOT, it will be counted as TN.
- If there is at least 1 lesion detected in an organ on ^{68}Ga -OPS202 scan but not on SOT, it will be counted as FP.

Example for a given subject, a given visit VX:

	At least one lesion detected by ^{68}Ga -OPS202 at Visit VX	At least one lesion detected by SOT	Type of lesion for analysis
Primary site of GEP-NET	No	Yes	FN
Lymph nodes	Yes	No	FP
Liver	Yes	Yes	TP
Bones	No	No	TN
Lungs	Yes	Yes	TP

Specificity will be calculated using the following formula:

$$\text{Specificity} = \frac{TN}{TN + FP}$$

In the example above, ^{68}Ga -OPS202 PET/CT assessment will have a specificity equal to 0.5 when compared to SOT.

Subject-based and lesion-based sensitivity along with organ-based specificity will be summarised using descriptive statistics for:

- each of the six combinations of injected peptide/radioactivity dose range
- each of the two peptide mass dose ranges
- each of the three radioactivity dose ranges

It will be also summarised using descriptive statistics for following five radioactivity dose groups:

- ^{68}Ga -OPS202 PET/CT at 40 to 80 MBq
- ^{68}Ga -OPS202 PET/CT at 100 to 140 MBq
- ^{68}Ga -OPS202 PET/CT at 160 to 200 MBq
- ^{68}Ga -OPS202 PET/CT at 100 to 200 MBq *
- ^{68}Ga -OPS202 PET/CT at 40 to 200 MBq *

Note: *A subjects' scan will use either his visit 2 or visit 3 scan, and not both. ^{68}Ga -OPS202 PET/CT at (100-200 MBq) and (40-200 MBq) will use the same subjects except the scan/visit with the lowest dose will be read. i.e.

- For 100-200 MBq, will choose Arm: A visit3, B visit2, C visit 2
- For 40-200 MBq, will choose Arm: A visit2, B visit2, C visit 3

Individual values of subject-based, lesion-based sensitivity and organ-based specificity will be listed by subject and by visit for this assessment (PET/CT).

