Any outlier identified prior to database lock which is impossible/implausible will be excluded from the analysis. For other identified outliers, the impact should be assessed by performing the statistical analysis with the actual values and at least one other analysis eliminating or reducing the outlier effect.

If any outliers are identified after database lock the statistical analysis should be performed with the actual values and at least one other analysis eliminating or reducing the outlier effect.

A search of outliers by Chiltern should be performed before the database lock and actions with the sponsor should be defined (e.g. edition of queries).

3.2.4 *Subject disposition*

The numbers and percentages of subjects included in each of the Screened, Randomised, Safety, PP and PK population will be tabulated in total and by randomisation arm. The reasons for subject exclusions from PP population will also be tabulated.

A listing of dates and time of assessments will be presented by subject for randomisation arm.

A summary table will be presented for each subject population presenting the number of subjects in each randomisation arm at each visit and identifying the number of subjects who withdrew from the study over time. A unique flow chart will be drawn with the number of subjects in each population.

3.2.5 *Withdrawals*

Discontinued subjects will be listed and a summary table of the number and percentage of subjects who completed and withdrew from the study and the reasons for withdrawal will be presented by randomisation arm and overall.

3.2.6 *Demographic and baseline characteristics*

In order to characterise the subjects, descriptive summary statistics (n, mean, SD, median, minimum, and maximum) or frequency counts of demographic and baseline data will be presented by randomisation arm (three sequences) and overall for the following populations:

- Randomised population
- PP population.

No statistical comparison of the randomisation arms will be performed.

Summary statistics will be provided for demographic and baseline characteristics:

- sex, race/ethnicity, age and age class
- height, weight at screening, body mass index (BMI) and BMI in categories at screening (refer to Appendix 1, Derived data)
- Eastern Cooperative Oncology Group (ECOG) performance status

Summary statistics of the tumour characteristics will be provided:

- site of primary tumour
- primary tumour resected
- time since diagnostic (refer to Appendix 1, Derived data)

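### Organ-based specificity (SAP 3.2.1.2 e) scores a known, unresected primary that PET/CT finds and CT misses as a false positive, so within a subject the dose that detects it scores lower

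*SAP*

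**What the plan says.** Organ-based specificity is defined in SAP 3.2.1.2 e) as TN/(TN + FP), organ by organ, for each PET/CT assessment.

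- **True negative:** the rule begins "If there are 0 lesions detected in an organ on both" the tracer scan and the standard of truth.
- **False positive:** a lesion on the tracer "scan but not on SOT, it will be counted as FP".
- **Organs:** the worked example for specificity has five rows, one of them the primary site. This matches the list given just before it for lesion-based sensitivity: "following organs will be analysed: Primary site of GEP-NET, Lymph nodes, Liver, Axial/appendicular skeleton, Lungs".
- **Worked example:** the "PET/CT assessment will have a specificity equal to 0.5 when compared to SOT".
- **Reference:** SAP 3.2.1.1 states "The SOT is the CT scan images acquired at Visit 2 and Visit 3", read for both timepoints together. SAP 3.2.1.2 f) confirms that the reference is not visit-specific, and applies the same method to the earlier sstr2 agonist scan.

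Three other places bear on the point.

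- SAP 3.2.1.2 c) says of the false-positive label that "without histology, this determination is equivocal". Section 5 repeats this; e) does not.
- SAP 3.2.6 summarises at baseline the site of the primary and whether the "primary tumour resected" item applies. Neither enters the specificity rule.
- The opening of SAP 3.2.1.2 says that selection of the optimal dose range "will be based on the provided descriptive statistics for all secondary and exploratory efficacy endpoints", in addition to the primary endpoint.

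The protocol's exploratory objective and endpoints name sensitivity, not specificity.

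**The concern.** Every subject has pathologically confirmed metastatic GEP-NET. Where the site of the primary is recorded and it has not been resected, disease at that site is known whatever CT shows. If PET/CT finds that primary and CT does not, the finding is right but is labelled FP. If PET/CT also misses it, the miss is labelled TN. For this organ in these subjects, both labels run the wrong way.

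This bears on the dose comparison because both of a subject's scans are judged against one pooled CT reference. The set of CT-negative organs is the same at Visit 2 and Visit 3, so any difference in specificity between the two scans comes from what PET/CT reported. A dose that brings out a CT-negative primary loses specificity relative to the same subject's other dose.

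The ratios restricted to the primary site give no offsetting credit. Per-organ relative lesion count (SAP 3.2.1.1) and sensitivity (3.2.1.2 e) need a CT lesion at that site. The all-organ relative lesion count does credit the finding. The same correct detection thus counts for a dose in one selection input and against it in another.

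**Working it through.** **Inputs.** The TN and FP rules, the formula and the worked example are in SAP 3.2.1.2 e). The pooled CT reference is in SAP 3.2.1.1. The 8 scans per dose combination are in SAP 1.2, Table 1.

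**1. The SAP's own figure.** The example has primary site FN, lymph nodes FP, liver TP, bones TN and lungs TP. Only TN and FP enter: 1/(1 + 1) = 0.5. This agrees with the SAP.

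**2. Change only the primary-site row of that example.**

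| Primary site | SAP rule | Primary site excluded |
|---|---|---|
| Unresected, PET/CT positive, CT negative | 1/(1 + 2) = 0.33 | 1/2 = 0.50 |
| Unresected, negative on both | 2/(2 + 1) = 0.67 | 1/2 = 0.50 |
| Resected, negative on both | 2/(2 + 1) = 0.67 | 1/2 = 0.50 |

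The scan that finds the primary scores half of what the scan that misses it scores. With the site excluded the two are equal.

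**3. General form.** Let a subject have m other CT-negative organs, of which t are also PET/CT-negative, with the same t at both scans, plus an unresected CT-negative primary. The detecting dose scores t/(m + 1), the missing dose (t + 1)/(m + 1). The gap is 1/(m + 1), whatever t is. With all m organs PET/CT-negative (t = m):

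| m | Detecting dose | Missing dose | Gap | Shift in an 8-scan cell mean, gap/8 |
|---|---|---|---|---|
| 1 | 0.50 | 1.00 | 0.50 | 0.063 |
| 2 | 0.67 | 1.00 | 0.33 | 0.042 |
| 3 | 0.75 | 1.00 | 0.25 | 0.031 |

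**4. Effect on a dose-group mean, under stated assumptions.** The documents do not give the share u of subjects with an unresected, CT-negative primary, or the detection rate at each dose. Assume u from 10% to 50%, detection of that primary of 90% at the better dose and 50% at the worse, and m from 1 to 3. The better dose's mean specificity is then lower by u × (0.90 − 0.50)/(m + 1):

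- smallest: 0.10 × 0.40/4 = 0.01
- largest: 0.50 × 0.40/2 = 0.10

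**5. Resected primary, negative at both visits.** One TN is added to each of the subject's scans. With n other CT-negative organs and t1 and t2 true negatives at the two scans, the within-subject difference changes from (t1 − t2)/n to (t1 − t2)/(n + 1). It shrinks but keeps its sign. The level rises: with one FP among two other CT-negative organs it goes from 1/2 = 0.50 to 2/3 = 0.67.

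**The case against.** The other side has a good deal on its side.

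- **Disclosure.** The SAP calls the FP label equivocal under c) and in Section 5, heads e) as preliminary, and presents specificity as relative to the standard of truth. The arithmetic is right for that definition. This stands, and a reader who inferred that the calculation is simply wrong would go too far. But the caveat is not carried into e), and it does not stop the figure being computed and used.
- **Resected primaries.** A reader might infer that counting an empty, resected site as TN is a second error against the better dose. The documents do not support that. The site is a valid negative, and step 5 shows that it only pads the level and dilutes contrasts. It could distort comparisons between arms only if resection were unbalanced across them.
- **Size.** A reader might take the one-third drop in a single scan as the expected bias. It is an illustration, because the number of subjects concerned is not given.
- **Is the finding truly correct?** Eligibility does not require a located primary or histology from it, and central readers are blinded to history. The Imaging Review Charter and SAP Appendix 1, which may say how foci are assigned to the primary site, were not available. The point is therefore confined to subjects with a recorded, unresected primary.
- **Weight in dose selection.** The first criterion is the highest relative lesion count, which rewards extra detection over all organs. There is no formal test, no stated weight for specificity, and no statement that higher specificity is better. This limits the consequence. It leaves the classification as it is, and the SAP still names all exploratory endpoints as a basis for selection.

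**Conclusion.** The concern holds for one defined case. When a recorded, unresected primary is CT-negative, the rule in e) counts its detection as FP and its omission as TN, so the better-detecting dose scores lower in the same subject: 2/3 against 3/3 with two other negative organs, or 0.33 against 0.67 in the SAP's own example with only the primary row changed. One such subject shifts an 8-scan cell mean by about 0.03 to 0.06, for one to three other CT-negative organs. The total effect cannot be derived from the documents; the range of 0.01 to 0.10 in step 4 rests wholly on assumed prevalence and detection rates.

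The measure is exploratory and descriptive, so the consequence is a misleading figure among the inputs to dose selection. The primary analysis is unaffected. CT is an imperfect negative reference for the other four organs too, but there the disease status is open. The primary site is the clear case because the trial's own baseline data can contradict the label.

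**What to change.** In SAP 3.2.1.2 e), and in f) where the same method is applied to the sstr2 agonist scan:

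1. Compute organ-based specificity on lymph nodes, liver, bone and lungs only, and remove the primary-site row from the specificity example. If the sponsor wants to keep the site in view, add a sensitivity display that treats a recorded unresected primary as disease-positive.
2. Repeat in e) the caveat from c) that a PET/CT-positive, CT-negative organ cannot be called false without histology.
3. State that this specificity is not a basis for selecting the dose range.

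Listing organ-based specificity in SAP Section 5 as an addition to the protocol would be tidy, but is presentational.

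The cost is a few lines of SAP text and one changed derivation from data already collected. The downside is one organ fewer in the denominator of an exploratory figure; a scan with CT lesions in all four remaining organs would have no specificity value.

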## 6 DIAGNOSTIC IMAGING OF SUBJECTS

### 6.1 Study Imaging Product

#### 6.1.1 Ga-OPS202

At Screening, subjects will be allocated a subject number. Following confirmation of eligibility for the study, subjects will be randomised to one of the following sequence of Ga-OPS202 peptide mass dose/ radioactivity dose ranges:

- Arm A: 5-20 µg/ 40-80 MBq at Visit 2 and 30-45 µg/ 100-140 MBq at Visit 3

or

- Arm B: 5-20 µg/ 100-140 MBq at Visit 2 and 30-45 µg/ 160-200 MBq at Visit 3

or

- Arm C: 5-20 µg/ 160-200 MBq at Visit 2 and 30-45 µg/ 40-80 MBq at Visit 3

Ga-OPS202 is a diagnostic medicinal product with three main components, namely:

- Ga, a positron emitter radionuclide with a half-life of 68 min
- NODAGA, a chemical chelator group, and
- JR11, an antagonist somatostatin analogue that binds to sst2 receptors

OPS202 (cold kit) is available for clinical trials in a 50 µg peptide dose vial, and is radiolabeled using a Ge/Ga-generator. Due to the short half-life (68 min) of the Ga radioisotope, on-site generation of Ga-labeled radiopharmaceuticals is mandatory. The Ga is eluted initially from the generator with hydrochloric acid and the eluate combined with the reconstituted peptide kit preparation. The radiolabelling occurs at room temperature. The product then undergoes radiopharmaceutical quality control (see Preparation, Radiolabeling and QC manual).

The radiolabelled OPS202 (Ga-OPS202) consists of 50 µg of peptide in a total volume of 6 mL (8.33 µg/mL). Sampling of 0.5 mL for QC yields 5.5 mL solution from which the volume to be administered is withdrawn. This volume to be injected is calculated to obtain the target peptide mass dose and the desired radioactivity dose.

The calculation of the volume takes into account the different components that determine the final radioactivity dose, the subject will be exposed to, in particular:

- The amount of Ga eluted from the generator which depends on the latter half-life
- The time elapsed between OPS202 (cold kit) radiolabelling and the injection of Ga-OPS202 to the subject (decay of Ga), the variation of which is a tool to adjust the final peptide/radioactivity dose required to be injected
- The required peptide mass dose and radioactivity dose of Ga-OPS202 to be injected.

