- Scatterplot of radioactivity dose/kg x SUV_{max}, per each of the four organs
- Scatterplot of radioactivity dose/kg x absolute number of lesions detected by ⁶⁸Ga-OPS202, per each of the five anatomic sites (Primary site of GEP-NET, Lymph nodes, Liver, Axial/appendicular skeleton (Bones), Lungs).
- Scatterplot of radioactivity dose/kg x difference between number of lesions detected by ⁶⁸Ga-OPS202 and number of lesion detected by SOT, per each of the five anatomic sites.

Besides, as categorical analysis of the radioactivity dose/kg, the following ranges will be used for the analysis, based on the observed distribution of the continuous radioactivity dose/kg among PP population:

- [min-Q1] MBq/kg
-]Q1-median] MBq/kg
-]median-Q3] MBq/kg
-]Q3-max] MBq/kg

Based on those ranges, summary tables with descriptive statistics for each of the four ranges of radioactivity dose/kg will be provided. Also, into each of the four ranges of radioactivity dose/kg, the two peptide doses will be analysed, that will lead to analyse, with same methodology as previously, 8 combinations of radioactivity dose/kg x peptide mass dose ranges.

Listings of individual values will be provided by ascending radioactivity dose/kg range then by ascending radioactivity dose/kg, and by subject (and by organ when applicable).

Exploratory efficacy endpoints:

- e) Preliminary diagnostic sensitivity of ⁶⁸Ga-OPS202 imaging of GEP-NETs by both subject-based and lesion-based analysis compared to standard-of-truth; and organ-based specificity, by radioactivity dose range (i.e. 40-80 MBq, 100-140 MBq, 160-200 MBq, 100-200 MBq, 40-200 MBq).

Diagnostic sensitivity between ⁶⁸Ga-OPS202 and SOT will be assessed using performance specified in table below.

Table 3 Diagnostic performance of ⁶⁸Ga-OPS202 compared to SOT

⁶⁸ Ga-OPS202 PET/CT scan results	SOT results	
	# of lesions detected	# of lesions not detected
# of lesions detected	True Positive (TP)	False Positive (FP)
# of lesions not detected	False Negative (FN)	True Negative (TN)

The sensitivity corresponds to the probability that the ⁶⁸Ga-OPS202 imaging detects the lesions, given that the lesions are positive in SOT.

For each PET/CT assessment, the sensitivity will be computed using following formula, per each of the organs (lesion-based approach) and overall (subject-based approach):

$$Sensitivity = \frac{TP}{TP + FN}$$

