f) Comparison to sstr2 agonist positive scan results will be computed for sensitivity analysis. In order to compare ^{68}Ga -OPS202 PET/CT to sstr2 agonist PET assessments, the two following analyses will be performed:

- Sensitivity and specificity of previously acquired sstr2 agonist PET versus SOT. Diagnostic sensitivity of previously acquired sstr2 agonist scan (at Visit 1) will be analysed by subject-based analysis and lesion-based approaches (per organ) compared to SOT.

Also, organ-based specificity will be computed.

Methodology for computing sensitivities and specificity will be same as described in e), with sstr2 PET instead of ^{68}Ga -OPS202 PET/CT assessments, compared to SOT.

As sstr2 agonist PET scan is performed only at Visit 1 and as SOT is not specific to V2 or V3, values of sensitivities/specificity will be unique per subject.

Subject-based and lesion-based sensitivity along with organ-based specificity will be summarised using descriptive statistics for all subjects.

Individual values of subject-based, lesion-based sensitivity and organ-based specificity will be listed by subject for this assessment (sstr2 PET).

- Comparison of sensitivity of ^{68}Ga -OPS202 PET/CT to previously acquired SSTR2 agonist PET.

The subject-based sensitivity of ^{68}Ga -OPS202 PET/CT will be compared to sensitivity of previously acquired SSTR2 agonist PET, both assessed vs SOT.

Therefore for each subject*visit, the difference will be computed as:

Sensitivity (PET/CT vs SOT) – Sensitivity (SSTR2 vs SOT).

Note that value of subject-based sensitivity (SSTR2 vs SOT) will be unique per subject.

This difference will be summarised using descriptive statistics for:

- each of the six combinations of injected peptide/radioactivity dose range
- each of the two peptide mass dose ranges
- each of the three radioactivity dose ranges

It will be also summarised using descriptive statistics for following five radioactivity dose groups:

- Difference of ^{68}Ga -OPS202 PET/CT (at 40 to 80 MBq) to SSTR2 PET
- Difference of ^{68}Ga -OPS202 PET/CT (at 100 to 140 MBq) to SSTR2 PET
- Difference of ^{68}Ga -OPS202 PET/CT (at 160 to 200 MBq) to SSTR2 PET
- Difference of ^{68}Ga -OPS202 PET/CT (at 100 to 200 MBq) to SSTR2 PET
- Difference of ^{68}Ga -OPS202 PET/CT (at 40 to 200 MBq) to SSTR2 PET

g) SUV_{max} ratio for lesions

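### Does the 40–200 MBq row of the exploratory sensitivity analysis mislead, given that it contains no 160–200 MBq scan?

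*SAP*

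**What the plan says.** SAP 3.2.1.2 e) opens by announcing results "by radioactivity dose range (i.e. 40-80 MBq, 100-140 MBq, 160-200 MBq, 100-200 MBq, 40-200 MBq". The last two groups are pooled and carry an asterisk. The note under them allows one scan per subject, from Visit 2 or Visit 3 but not both. It adds that the two pooled groups "will use the same subjects except the scan/visit with the lowest dose will be read". It then lists the visits for each group. For the wider one the list is "For 40-200 MBq, will choose Arm: A visit2, B visit2, C visit 3".

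Protocol 6.1.1 gives the activities behind those visits:

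- Arm A: "40-80 MBq at Visit 2 and 30-45" µg with 100–140 MBq at Visit 3.
- Arm B: "100-140 MBq at Visit 2 and 30-45" µg with 160–200 MBq at Visit 3.
- Arm C: 160–200 MBq at Visit 2, then "40-80 MBq at Visit 3".

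SAP 3.2.1.2 f) takes the difference in sensitivity between OPS202 PET/CT and the earlier agonist PET, computed for every subject and visit, and summarises it for the same five groups. The last of them is "PET/CT (at 40 to 200 MBq) to SSTR2 PET", with neither asterisk nor note. Part f) also states: "Note that value of subject-based sensitivity (SSTR2 vs SOT) will be unique per subject".

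**The concern.** A row headed 40 to 200 MBq stands in a list with rows whose labels do state the doses summarised. A reader could take it as performance across the whole studied range, yet two thirds of its scans are in the lowest range and none is in the highest. Protocol 1.5 itself expects the lowest range to be near or below optimal for some subjects. If sensitivity rises with activity, the row sits below an average over all scans.

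Part f) carries the label into the comparison with the agonist PET. Each subject has a single agonist value, so if the rule of e) applies there, a lower OPS202 figure passes straight into the difference. SAP 3.2.1.2 also lets exploratory statistics contribute to the choice of dose range. At stake would be an understated sensitivity, and an understated advantage over the agonist, under a heading that suggests full coverage.

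**Working it through.** **Inputs.** The activity ranges by arm and visit come from Protocol 3.3 (Table 4) and 6.1.1. The 8 per-protocol subjects per arm come from SAP 2.1.2. The selection rule and visit lists come from SAP 3.2.1.2 e).

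**Reproducing the visit lists.** Take each subject's lowest-activity scan within the labelled range.

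| Arm | Visit 2 (MBq) | Visit 3 (MBq) | Chosen for 40–200 | Chosen for 100–200 |
|---|---|---|---|---|
| A | 40–80 | 100–140 | Visit 2 | Visit 3 |
| B | 100–140 | 160–200 | Visit 2 | Visit 2 |
| C | 160–200 | 40–80 | Visit 3 | Visit 2 |

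Both columns match the lists in the SAP, so the rule and the lists agree.

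**Content of the pooled rows, 8 scans per arm.**

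- 40–200 row: 8 + 8 = 16 scans at 40–80, 8 at 100–140, 0 at 160–200. The planned span is 40–140 MBq.
- 100–200 row: 8 + 8 = 16 scans at 100–140 and 8 at 160–200. The planned span is 100–200 MBq.
- Mean of the range midpoints, 40–200 row: (60 + 120 + 60)/3 = 80 MBq. For all 48 scans it is (60 + 120 + 180)/3 = 120 MBq.

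**How far the row could lie from an equal mix.** Let a, b and c be the sensitivities at 40–80, 100–140 and 160–200 MBq, with no peptide or visit effect.

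- 40–200 row: (2a + b)/3. All 48 scans: (a + b + c)/3. Difference: (a − c)/3.
- 100–200 row: (2b + c)/3. All 32 scans in that range: (b + c)/2. Difference: (b − c)/6.

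The documents give no values for a, b and c, so the rise from lowest to highest range has to be assumed:

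| Assumed rise c − a (points) | Difference for the 40–200 row (points) |
|---|---|
| 0 | 0 |
| 10 | −3.3 |
| 20 | −6.7 |
| 30 | −10.0 |

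These figures compare the row with a quantity that the SAP does not set out to estimate. The SAP specifies one scan per subject at the lowest dose, and (2a + b)/3 is exactly that.

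**Part f).** If the one-scan rule carries over, the 40–200 row has 24 values. If every subject-by-visit difference enters, it has 16 + 16 + 16 = 48, includes the 160–200 MBq scans, and its label is literally correct. For 100–200 MBq the counts are 24 or 16 + 16 = 32. With 8 subjects per arm, each subject's agonist value enters the 40–200 row once or twice, so its mean is the same either way. The gap between the two readings of that row is again (a − c)/3.

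**The case for a change.** The best case for a change rests on f). Part e) discloses its rule, but f) has no asterisk, note or cross-reference for the pooled groups. Its one pointer back to e) concerns how the agonist's sensitivity and specificity are computed, not which OPS202 scan enters a group. Because f) forms a difference at each visit, two programmers could both claim to follow it and produce 24 or 48 values. The label in e) is also loose: disclosure makes the row programmable without making its heading describe its content. Repeating one note would cost almost nothing.

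Both observations stand as matters of drafting. Neither shows a wrong result. Part f) introduces its five dose groups just as e) does and gives them the same ranges, and e) is the only place where the pooled ones are defined, so carrying the definition forward is the natural reading. The number of observations is part of every descriptive summary (SAP 3.2.1.1 and 3.2.14), so the output will show 24 or 48.

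The link to dose selection is weak, because a row that pools ranges cannot rank them. The six combinations, two peptide ranges and three radioactivity ranges are each summarised separately in both e) and f), and e) lists individual sensitivities by subject and visit. Renaming only the wider row would also be uneven: the 100–200 row follows the same rule and leaves out Arm B's 160–200 MBq scans.

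**Conclusion.** The description of the row is accurate: 16, 8 and 0 scans in the three ranges, under a label that names the range selected from. It does not call for a change to the plan. In e) the selection is intentional, disclosed beside the row and reproducible, and a new label would leave every number as it is. In f) the missing note is a gap that an analyst fills from e).

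The 3.3 to 10 points for assumed rises of 10 to 30 points are not the size of an error. They show how a lowest-dose scan would differ from an equal mix if there were a dose effect, and they are zero if there is none. Their effect on the agonist comparison depends on the rule of e) carrying over to f).

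The conclusion assumes the planned 8 evaluable subjects per arm, each dosed within the assigned ranges. Whether the output tables carry the note cannot be checked, because the templates are in SAP Appendix 2, which is not among the documents. Nothing is tested (SAP 3.1.5), and the primary analysis does not use these rows.
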